11.1 Adverse Events

11.1.1 Adverse Events listings

A table of Adverse Event listings will be produced with the following headings:

- Participant ID:
- Randomised assignment:
- Adverse Event Number:
- AE term: 1=Headache 2=Vertigo 3=Seizures 4=Abdominal pains with nausea 5=Abdominal pains without nausea 6=Nausea without abdominal pains 7=Diarrhoea 8=Rash 9=Pruritus 10=Facial oedema 11=Urticaria 12=Vomiting 13=Other
- Date of Onset: DD/MM/YYYY
- Date of resolution: DD/MM/YYYY
- Outcome: 1=Resolved without Sequelae 2=Resolved with Sequelae
 3=Ongoing 4=Death 5=Unknown
- Severity:
- Seriousness: 0=Not Serious 1=Resulted in death 2=Life-threatening 3=Required inpatient or prolonged existing hospitalisation 4=Resulted in persistent or significant disability/incapacity 5=Resulted in congenital anomaly/birth defect 6=Other Important Medical Event, please specify
- Causality: 1=Definitely related 2=Probably related 3=Possibly related 4=Unlikely to be related 5=Not Related
- Treatment: Y/N

Listings will be ordered by subject ID and timepoint.

11.1.2 Adverse Events summary statistics

Summary statistics of the frequency and percentage of AE's will be presented by treatment arm and time point for all treatment time points. Note that not all treatment arms treated at every time point thus Adverse Events information will not be reported unless treatment has occurred in error. Summary statistics will be provided for:

- all adverse events grouped
- for each Averse Event term (1–13) separately
- AE's grouped by system i.e. Neurological and Digestive

Comparisons of the frequency of adverse events between treatment arms can be made at baseline, 12 months and 24 months. The relative risk comparing the treatment arms separately to the control arm and comparing the two treatment arms to each other for an AE grouping will be presented if the number of adverse events is > 10% for any treatment arm.

Dot plots will be used to show the frequency, percentage and relative risk for each of the 3 treatment arm comparisons at each time point.

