9.5 Treatment Compliance

Information relating to the number of participants who missed the IMP at the required visit captured in the 'Non-Adherence to protocol' CRF as well as the 'IMP administration' CRF will be shown in a summary table and displayed as a stacked bar chart, each treatment group represented by their colour and position within the stack. The number missing will be a scale on the y axis and each treatment time—point will be ordered on the x axis.

- · Standard of Care Arm: Baseline, 12 months and 24 months
- Intervention Arm 1 (2 x treatment): Baseline, month 7, month 12, month 19 and month 24
- Intervention arm 2 (4 x treatment): Baseline, month 4, month 7, month 10, month 12, month 16, month 19, month 22 and month 24

Information relating to the number of participants who missed data collection visits captured in the 'Non-Adherence to protocol' CRF will be shown in a summary table and displayed using a stacked bar chart with each treatment arm represented by their colour and position within the stack, the number missing will be shown on the y axis and time-point on the x axis.

- Ultrasonography
- Parasitology
 - Standard of Care Arm: Baseline and 24 months
 - o Intervention Arm 1: Baseline and 24 months
 - o Intervention arm 2: Baseline and 24 months

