10.3 Exploratory Efficacy Analyses

10.3.1 Complier Average Causal Effect analysis

To investigate how treatment compliance affects the primary outcome CACE (Complier Average Causal Effect) analysis will be performed (17) to compare each intervention arm separately to the control arm.

The CASE will be calculated using the ITT treatment effect and the proportion of compliers in the treatment arms, different levels of compliance will be used and are defined below for each intervention arm:

Intervention arm 1: Participants who take ≥ 4 doses of the PZQ out of a maximum of 5 possible doses.

Intervention arm 2: Participants who take ≥ 8 doses of the PZQ out of a maximum of 9 possible doses.

AND

Intervention arm 1: Participants who take > the baseline i.e. the control arm dose of PZQ (2 doses)

Intervention arm 2: Participants who take > intervention arm 1 dose of PZQ i.e. 5 doses

CASE calculation:

Intention To Treat (ITT) treatment effect
proportion of compliers in the intervention arm

The CACE estimation relies on the following assumptions:

- Treatment assignment is random
- Merely being offered the treatment has no effect on the outcomes
- If participants in the control arm had been randomised to the intervention arm, they would comply with the intervention at the same rate as those actually randomised to the intervention
- There is an absence of defiers patients that take the opposite treatment to what is offered
- Stable Unit Treatment Value Assumption (SUTVA). SUTVA requires that the response of a particular participant depends only on the treatment to which the participant was assigned, not the treatments of others.

If these assumptions hold we can also estimate the potential outcomes among participants in the control arm using simple algebra.

'Complier' and 'Non-complier refer specifically to compliance to the intervention and participants in the control arm are assumed to receive the control treatment as intended and values therein are based on the aforementioned assumptions.

This analysis will also be performed for the secondary outcome of infection intensity:

- o mean epg
- Heavy infection

11 Safety Analyses

The safety population will be used for all safety analysis.

Safety data collected on the day of treatment and at 24 hours will be grouped for each time point, i.e. AE's from day 1 and \pm 24 hours will be grouped for baseline AE's and any repetitions will not be counted within the time-point.

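### Adverse events are compared between arms only at the three visits where every arm is scheduled one dose, and no per-child summary over all dosing visits is planned (cheap improvement, low severity)

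*SAP*

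**What the plan says.** Section 11.1.2 of the SAP plans AE frequencies and percentages "presented by treatment arm and time point for all treatment time points". It adds that "Comparisons of the frequency of adverse events between treatment arms can be made at baseline, 12 months and 24 months". Relative risks for each pair of arms are shown where AEs exceed 10% in any arm.

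Section 9.5 gives the dosing schedule. Control children are dosed at the start and again after one and two years. The 2x arm has those three doses plus one at month 7 and one at month 19. For the 4x arm the listed visits are "Baseline, month 4, month 7, month 10, month 12, month 16, month 19, month 22 and month 24".

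The opening of section 11 says that safety data come from the treatment day and 24 hours later, are grouped by time point, and are not counted twice within a time point. Section 11.1.2 also says that an arm not treated at a visit has no AE information reported for it, unless it was treated in error.

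The other AE analyses are also tied to single visits. The exploratory AE endpoints (5.2.2), the ROC curves (11.1.3.1), the logistic regressions (11.1.3.2) and the serious AE summary (11.2) all use baseline and 24 months. Section 11.1.1 lists individual AEs with participant ID and randomised arm. No section plans a per-child or whole-trial AE summary by arm.

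**The concern.** The trial asks what happens when praziquantel is given more often. Efficacy is compared by regimen, so a reader will want to set the AE burden of each regimen beside it. The planned relative risks do not supply that. At baseline the arms have been treated alike, so any difference is essentially chance, apart from any effect of open-label awareness. At 12 and 24 months they compare one dose with one dose, after different numbers of earlier doses.

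The per-dose comparison is worth having. Shown alone and unlabelled, though, a relative risk of 1 or below could be taken as a statement about the whole regimen, when the arm concerned may have recorded the most AEs. This is plausible if AE risk follows infection intensity, a link the SAP explores in section 11.1.3, because the more-treated arms might carry fewer eggs by 12 and 24 months.

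**Working it through.** **1. Dose counts and common visits (section 9.5).** Control: months 0, 12, 24, which is 3 doses. 2x arm: months 0, 7, 12, 19, 24, which is 5. 4x arm: months 0, 4, 7, 10, 12, 16, 19, 22, 24, which is 9. The last two agree with the maxima in section 10.3.1 ("Participants who take ≥ 4 doses of the PZQ out of a maximum of 5 possible doses" and "Participants who take ≥ 8 doses of the PZQ out of a maximum of 9 possible doses"). The visits common to all arms are months 0, 12 and 24, exactly those named in section 11.1.2.

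**2. Scheduled doses outside any comparison with control.** Control 0 of 3; 2x arm 2 of 5 (40%; months 7 and 19); 4x arm 6 of 9 (67%; months 4, 7, 10, 16, 19 and 22).

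**3. Illustration with equal risk per dose.** The SAP gives no AE rate, so the per-dose risk p is assumed. Also assumed are full dosing and, for the percentages, independence between doses within a child. With k doses, expected affected visits per child = k × p, and P(at least one AE) = 1 − (1 − p)^k. The relative risk at each compared visit is p/p = 1.0 throughout.

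| p assumed | At least one AE: 1x / 2x / 4x | Ratio 4x to 1x | Extra affected visits per child: 2x, 4x |
|---|---|---|---|
| 5% | 14.3% / 22.6% / 37.0% | 2.59 | 0.10, 0.30 |
| 10% | 27.1% / 41.0% / 61.3% | 2.26 | 0.20, 0.60 |
| 20% | 48.8% / 67.2% / 86.6% | 1.77 | 0.40, 1.20 |
| 30% | 65.7% / 83.2% / 96.0% | 1.46 | 0.60, 1.80 |

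Affected visits per child stand in the ratio 5/3 = 1.67 (2x) and 9/3 = 3.0 (4x) whatever p is.

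**4. Illustration with falling risk.** Suppose 20% per dose, and that every dose after the first in the 4x arm carries half that risk. The relative risk at 12 and 24 months is 0.10/0.20 = 0.50. Affected visits per child are 0.2 + 8 × 0.1 = 1.0 in the 4x arm against 3 × 0.2 = 0.6 in control, a ratio of 1.67. At least one AE: 1 − 0.8 × 0.9^8 = 65.6% against 1 − 0.8^3 = 48.8%.

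**5. What the visit tables can and cannot give.** Counts add across visits. The percentage ever affected does not, because the same children recur. With 10% affected at each visit, the percentage ever affected in the 4x arm could lie anywhere from 10% (the same children each time) to 9 × 10% = 90% (different children each time). In control it could lie from 10% to 3 × 10% = 30%. The tables do not say where, and they do not carry the within-child correlation that a valid interval needs.

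**6. Control dose count.** Section 10.3.1 puts the control arm at 2 doses, beside maxima of 5 and 9, whereas section 9.5 schedules 3. Taking 2, 5 and 9 as section 10.3.1 has them, the ratios in step 3 become 5/2 = 2.5 and 9/2 = 4.5. Leaving the month-24 dose out of every arm gives 2, 4 and 8, and ratios of 2.0 and 4.0. The point does not depend on which count is used, but the two sections must be reconciled.

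**The case against.** The SAP does not set regimen-level AE burden as a target. Its only AE objective (5.1.3) is how well infection intensity predicts AEs, and the AE endpoints are exploratory. Months 0, 12 and 24 are also the only scheduled visits at which all arms are asked about AEs in the same way, so restricting the comparison to them has a sound reason. Both points stand. A reader might infer that section 11.1.2 is an error or claims to measure the regimens' safety; the text does not support that.

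A second objection is that nothing is lost: counts can be summed from the visit tables, and the listing in 11.1.1 identifies each child. This stands for event totals. The listing also means that the missing figures could be derived, but no such derivation or comparison is planned.

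The third objection is the strongest. AEs are sought only around dosing, so the control arm has no scheduled AE observation at the six extra visits. If every recorded symptom were background, at the same rate b per visit, and the drug caused none, a rate model with log follow-up time as offset would still return 9b/3b = 3.0 and 5b/3b = 1.67. It would treat unobserved control time as event-free. This stands in full. A reader might take the ratios in the working as drug harm, but they cannot be separated from the number of times children were asked.

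Finally, the percentages are illustrative. Clustering of AEs within children would lower them, and section 16.1.2 says that many children were not treated at baseline, so full dosing did not occur.

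**Conclusion.** The concern holds as a reporting gap. The planned relative risks describe single-dose tolerability at 12 and 24 months, and essentially chance at baseline. The extra doses, 40% of the 2x schedule and 67% of the 4x schedule, enter no comparison with control. Neither the percentage of children ever affected nor a valid interval for a cumulative difference is planned, and neither can be recovered from the visit tables.

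The dose counts rest on section 9.5. The illustrated sizes rest on an assumed per-dose risk, independence between doses and full dosing; none of these comes from the document. No efficacy result or error rate is affected, and no AE data are lost. This is a cheap improvement of low severity.

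**What to change.** Add one table to section 11.1.2 for the safety population, by arm over all dosing visits, for any AE and by system group:

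- number and percentage of children with at least one AE;
- AEs (or affected dosing visits) per child;
- AEs per dose given, which separates tolerability from the number of doses.

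Give 2x v 1x and 4x v 1x differences with 95% CIs that allow for repeated events within a child, for example by a bootstrap over children or robust standard errors clustered on the child. Do not use a rate model with log follow-up time as offset.

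Label the 12- and 24-month relative risks as per-dose tolerability. State beside the cumulative figures that they include background symptoms, recorded more often in the more-dosed arms because those children are asked more often. Reconcile the control dose count between sections 9.5 and 10.3.1. If data have been seen, label the addition post hoc, as section 16.1.5 does for two other analyses.

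The cost is a few lines of SAP text and one table from data already collected.

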11.1.3 Analysis of adverse events and infection intensity

11.1.3.1 Exploratory analysis of Adverse Events and Infection Intensity: ROC curves

This analysis will produce Receiver Operator Characteristics (ROC) curves (18) to graphically represent the connection between clinical sensitivity and specificity for every possible cut off of infection intensity (epg) as a 'test' for predicting Adverse Events.

Adverse Events will be considered as follows:

- 1. Any adverse event (1-13) experienced, as either having an AE or not (Y/N)
- 2. Any digestive adverse event (4, 5, 6, 7 or 12) as either having an AE or not (Y/N)
- 3. Any neurological adverse event (1, 2, 3, 8, 9 or 11) as either having an AE or not (Y/N)

For each ROC curve the Area under the ROC will be calculated to provide an estimate of the efficiency of using infection intensity (epg) in predicting AE occurrence.

ROC curves will be produced for baseline and 24 month time points.

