5.2.2 Exploratory endpoints

- Schistosoma mansoni Egg Reduction Rate (ERR) measured between:
 - Point Baseline and baseline +4 weeks
 - Baseline and 2 years + 4 weeks
 - o 2 years and 2 years +4 weeks
- Prevalence at 2 years post 1st treatment.
- Cure rate between:
 - Baseline and baseline +4 weeks
 - o Baseline and 24 months
 - Baseline and 24 months +4 weeks
- Adverse Events measured at baseline and 24 months:
 - Any AE (Yes/No)
 - Digestive AE's = 4,5,6,7,or 12 on CRF see Also section 11 of SAP (Yes / No)
 - Neurological AE's 1,2,3,8,9 or III on CRF see Also section 11 of SAP (Yes/No)

[figure not shown]
6 Study Methods

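### The 'neurological' adverse event group mixes neurological with skin/hypersensitivity terms, and facial oedema is in neither system group

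*SAP*

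**What the plan says.** Section 11.1.1 fixes the adverse event codes. The list opens with "1=Headache 2=Vertigo 3=Seizures 4=Abdominal pains with nausea" and closes with "8=Rash 9=Pruritus 10=Facial oedema 11=Urticaria 12=Vomiting 13=Other".

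Section 11.1.3.1 sets three outcomes for the ROC curves of infection intensity as a predictor of adverse events, at baseline and at 24 months:

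- "Any adverse event (1-13) experienced, as either having an AE or not (Y/N"
- "Any digestive adverse event (4, 5, 6, 7 or 12) as either having an AE or not (Y/N"
- "Any neurological adverse event (1, 2, 3, 8, 9 or 11) as either having an AE or not (Y/N"

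The exploratory endpoints in section 5.2.2 define the neurological outcome in the same way: "Neurological AE's 1,2,3,8,9 or III on CRF see Also section 11 of SAP (Yes/No". The last code there is garbled in the copy at hand and is most likely 11.

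Section 11.1.2 plans frequencies and percentages by arm and time point for all events together, for each of the 13 terms separately, and for "AE's grouped by system i.e. Neurological and Digestive". It gives no codes for these two systems. A relative risk "for an AE grouping will be presented if the number of adverse events is > 10% for any treatment arm".

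**The concern.** The SAP says that it groups events by body system, yet the group it calls neurological contains rash, pruritus and urticaria. It gives no reason for this. The one remaining skin/hypersensitivity term, facial oedema, is left out of both system groups, although section 6.2.2 treats a history of that reaction to praziquantel as grounds for exclusion.

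Estimating how well infection intensity predicts adverse events is a stated exploratory objective (section 5.1.3). The AUC answers that question only for the outcome it is computed on. Under the present definition, a result labelled neurological would describe how well egg count predicts a composite of two kinds of event. In the by-system summary, a difference between arms in skin reactions could be read as a difference in neurological toxicity. No system group would show the four skin/hypersensitivity terms together.

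**Working it through.** The SAP states no figure to reproduce. The check maps each code in section 11.1.1 to the groups in sections 5.2.2 and 11.1.3.1.

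| Group in the SAP | Codes | Terms |
|---|---|---|
| Neurological | 1, 2, 3 | headache, vertigo, seizures |
| Neurological | 8, 9, 11 | rash, pruritus, urticaria |
| Digestive | 4, 5, 6, 7, 12 | abdominal pain with or without nausea, nausea alone, diarrhoea, vomiting |
| Neither | 10, 13 | facial oedema, other |

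1. **Neurological group.** 3 of 6 codes are neurological terms and 3 of 6 are skin/hypersensitivity terms. No neurological term in the list is left out.
2. **Digestive group.** All 5 codes are digestive, so the grouping by system is followed strictly there.
3. **Coverage.** 6 + 5 = 11 of 13 codes are assigned. The two left over are 10 and 13. Code 10 is therefore the only named term in neither group.
4. **Skin/hypersensitivity terms.** Of codes 8 to 11, three are counted as neurological and one is in no system group.
5. **Misprint or intention?** Codes 8 and 9 are legible in both 5.2.2 and 11.1.3.1, so a single slip or a PDF reading error does not explain the list.

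The effect on the outputs can be written down, though not evaluated. In a given arm and time point, let *n* be the proportion of children with at least one of codes 1, 2, 3, and *s* the proportion with at least one of 8, 9, 11 but none of 1, 2, 3.

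- **Reported rate** = *n* + *s*, of which *s* / (*n* + *s*) are children with no neurological term.
- **Relative-risk trigger** (if 11.1.2 uses the same codes, and reading its threshold as a percentage of children): the neurological relative risk is shown when *n* + *s* > 10% in any arm. Skin-only cases can therefore trigger it even where *n* is at or below 10% in every arm.
- **AUC.** Here *n* and *s* are taken over all children in the ROC analysis. The AUC is the probability that a random case has a higher egg count than a random non-case (ties counted half). The composite AUC is therefore (*n*·A_N + *s*·A_S) / (*n* + *s*), where A_N and A_S compare the two kinds of case with children who have none of the six codes. It can lie above or below the AUC for codes 1, 2, 3 alone, so the direction of the distortion is not known in advance.

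The SAP gives neither *n* nor *s*, nor any AUC.

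**The case against.** The strongest reply is that little is hidden. Section 11.1.2 tabulates each of the 13 terms by arm and time point. Section 11.1.1 lists every event with its severity, seriousness and causality. Section 11.2 reports serious events without reference to system groups. Rash, pruritus, facial oedema and urticaria are each visible. The affected endpoint and ROC curve are exploratory, and the by-system table is descriptive. Section 11.1.2 also names the two systems without codes, so its use of the same set is an inference.

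Most of this stands, and it limits the point. Per-term tables do not, however, correct an endpoint, an AUC or a relative risk that carries the wrong label. The inference about 11.1.2 is the natural one, since the SAP offers no other definition and 5.2.2 refers the reader to section 11, but it remains an inference.

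Nor does a deliberate composite rescue the definition. If the sponsor meant to combine neurological and allergic reactions, the label is wrong and leaving out facial oedema is unexplained.

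A reader might infer three stronger things that the SAP does not support:

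- *That the neurological outputs do not measure neurological events.* They do, since all three neurological codes are in the group. They measure them mixed with skin events.
- *That facial oedema drops out of safety reporting.* It is missing only from the two system groups.
- *That half of the reported neurological cases would be skin cases, because half of the codes are.* The terms need not be equally common and a child may have both kinds, so the count of codes says nothing about the share of cases.

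**Conclusion.** The definition is wrong as written and easy to correct. By the SAP's own code list, the exploratory neurological endpoint in 5.2.2 and its ROC curve and AUC in 11.1.3.1 would present a neurological-plus-skin composite as neurological. The by-system table and its relative risks in 11.1.2 share the fault on the likely but unstated reading that they use the same codes.

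The size that the document supports is a count: 3 of 6 codes misplaced, and 1 named term in neither system group. The effect on rates, relative risks or AUC cannot be computed from the SAP.

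The conclusion rests only on rash, pruritus and urticaria being skin/hypersensitivity rather than neurological terms, and on reading the garbled last code in 5.2.2 as 11. The importance is modest: primary and secondary efficacy, the any-event and digestive ROC curves, the any-event logistic regression in 11.1.3.2, the per-term tables and serious event reporting are untouched.

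**What to change.** - Define neurological as codes 1, 2, 3. Keep digestive as 4, 5, 6, 7, 12.
- Summarise codes 8, 9, 10, 11 as a separate skin/hypersensitivity group in the by-system table. Leave 13 (other) outside the system groups, or classify it case by case.
- Obtain medical sign-off on the grouping.
- State the codes in 11.1.2, and use the same definitions in 5.2.2, 11.1.2 and 11.1.3.1.
- Record the change in section 16, as post hoc if it is made after data were seen. The SAP already marks other post hoc decisions in this way.

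A ROC curve for the skin/hypersensitivity group is optional, and with few events it may be uninformative. If the sponsor wants to keep the composite, the minimum is to relabel it, give the reason and say where facial oedema belongs.

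The cost is SAP wording and a recode of data already collected. The statistical price is fewer events in the neurological group, hence a less precise AUC and relative risk, and possibly no relative risk if the group no longer passes the 10% threshold.
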